# 9.5 Reporting Period

Study doctors will assess for adverse events or reactions at each visit and can be alerted by email or telephone by the ward staff, the patient will be assessed as soon as is practical and within 12 hours of the alert. The reporting period for AE and SAEs starts from the date and time of consent, and the reporting period for AR, SAR, and SUSARs starts from the first IMP dose regardless of treatment allocation (ACZ or SoC). The monitoring period for events will be from 5 days from baseline but data on all adverse events will be collected up to the point of discharge from the written and electronic medical record.

# 9.6 Responsibilities

The responsibilities regarding AE and AR reporting as follows:

#### Principal Investigator (PI):

- 1. Checking for AEs and ARs when participants undergo retreatment and at follow-up.
- 2. Using medical judgement in assigning severity, seriousness and causality.

3. Ensuring that all SAEs and SARs are recorded and reported in line with the requirements of the protocol and SUSARs are recorded and reported to the Sponsor within 24 hours of becoming aware of the event and provide further follow-up information as soon as available.

Ensuring that SAEs and SARs (including SUSARs) are chased with Sponsor if a record of receipt is not received within 2 working days of initial reporting.

4. Ensuring that AEs and ARs are recorded and reported in line with the requirements of the protocol.

5. Preparing the clinical sections and final sign off of the Development Safety Update Report (DSUR).

Sponsor:

A medical R&D Director will assess causality and expectedness of behalf of the Sponsor:

1. Clinical oversight of the safety of patients participating in the trial, including an ongoing review of the risk/benefit.

2. Using medical judgement in assessing, causality of SAEs.

3. In order to assess expectedness, the R&D Director will need to check if the SAR is listed in the Reference Safety Information (RSI). If the SAR is listed in the RSI then it is expected. If the event is not listed in the RSI then it is unexpected and is a SUSAR and subject to expedited reporting to the MHRA and REC.

4. Immediate (within 24 hours) review of all SUSARs.

5. Review of specific SAEs and SARs in accordance with the trial risk assessment and protocol as detailed in the Trial Monitoring Plan.

6. Central data collection and verification of AEs, ARs, SAEs, SARs and SUSARs according to the trial protocol.

7. Reporting safety information to the Sponsor Oversight Group for the ongoing assessment of the risk / benefit according to the Trial Monitoring Plan.

8. Expedited reporting of SUSARs to the Competent Authority (MHRA in UK) and REC within required timelines.

9. Notifying Investigators of SUSARs that occur within the trial.

10. Checking for (annually) and notifying the PI of updates to the Reference Safety Information for the trial.

11. Preparing standard tables and other relevant information for the DSUR in collaboration with the PI and ensuring timely submission to the MHRA and REC.

# Table: Serious adverse event report

Severity Assessed by the Co-I and PI or just PI	The assessment of severity of an SAE will be based on the investigator's clinical judgement using the following definitions: Mild : An event that is easily tolerated by the trial subject, causing minimal discomfort, and not interfering with everyday activities. Moderate: An event that is sufficiently discomforting to interfere with normal everyday activities. Severe: An event that prevents normal everyday activities.
Seriousness Assessed by the Co-I and PI or just PI	An event is considered serious if it meets one or more of the following criteria: (a) results in death (b)life-threatening (c) requires hospitalisation or prolongation of existing hospitalisation (d) results in persistent or significant disability or incapacity (e) consists of a congenital anomaly or birth defect. Important medical events that may not be immediately life- threatening or result in death or hospitalisation but may jeopardise the patient or may require intervention to prevent one of the outcomes listed in the definition above should also be considered serious.

Causality Assessed by the Co-I and PI or just PI	
 
The investigator will assess whether the SAE is likely to be related to the IMP according to the following definitions:
 
Unrelated: Where an event is not considered to be related to the IMP.
 
Possibly related: The nature of the event, the underlying medical condition, concomitant medication, or temporal relationship make it possible that the SAE has a causal relationship to the study drug.
 

Expectedness Assessed by the R&D Director (on behalf of the Sponsor) for single-site trials	To assess expectedness, the R&D Director will need to check if the SAR is listed in the Reference Safety Information (RSI). The RSI for IMPs with a marketing authorization (MA) is section 4.8 (Undesirable Effects) of the MHRA approved Summary of Product Characteristics (SmPC) or for IMPs without an MA, the RSI is the relevant section in the Investigator Brochure (IB). If the SAR is listed in the RSI then it is expected. If the event is not listed in the RSI then it is unexpected and is a SUSAR and subject to expedited reporting to the MHRA and REC.

# 9.7 Notification of deaths

The average in-patient mortality rate for patients admitted to hospital with heart failure is 10%, the 30day mortality of those surviving to discharge is 25%. Thus we expect up to 4 patients to die in hospital and a further 5 to die in the month following discharge. We may expect further deaths up to the 180 day follow up point. We will report all deaths to the sponsor, all in-patient deaths will be reported within 24 hours, all out-patient deaths will be reported at 30 and 180 days.

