# 9 PHARMACOVIGILANCE

#### 9.1 Definitions

Term	Definition
Adverse Event (AE)	Any untoward medical occurrence in a participant to whom a medicinal product has been administered, including occurrences which are not necessarily caused by or related to that product.
Adverse Reaction (AR)	An untoward and unintended response in a participant to an investigational medicinal product which is related to any dose administered to that participant.
	The phrase "response to an investigational medicinal product" means that a causal relationship between a trial medication and an AE is at least a reasonable possibility, i.e. the relationship cannot be ruled out.
	All cases judged by either the reporting medically qualified professional or the Sponsor as having a reasonable suspected causal relationship to the trial medication qualify as adverse reactions.
Serious Adverse Event (SAE)	
 
A serious adverse event is any untoward medical occurrence that:
 
results in death
 
is life-threatening
 
requires inpatient hospitalisation or prolongation of existing hospitalisation
 
results in persistent or significant disability/incapacity
 
consists of a congenital anomaly or birth defect
 
Other 'important medical events' may also be considered serious if they jeopardise the participant or require an intervention to prevent one of the above consequences.
 
NOTE: The term "life-threatening" in the definition of "serious" refers to an event in which the participant was at risk of death at the time of the event; it does not refer to an event which hypothetically might have caused death if it were more severe.
 

Serious Adverse Reaction (SAR)	An adverse event that is both serious and, in the opinion of the reporting Investigator, believed with reasonable probability to be due to one of the trial treatments, based on the information provided.
Suspected Unexpected Serious Adverse Reaction (SUSAR)	
 
A serious adverse reaction, the nature and severity of which is not consistent with the information about the medicinal product in question set out:
 
in the case of a product with a marketing authorisation, in the summary of product characteristics MHRA approved (SmPC) for that product
 
in the case of any other investigational medicinal product, in the investigator's brochure (IB) relating to the trial in question
 

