# 9.2 Operational definitions for (S)AEs

Due to the pilot and exploratory nature of this study **all** adverse events and adverse reactions will be recorded. All serious adverse events serious adverse reactions, and suspected unexpected serious adverse reactions will be reported.. This will enable collection on safety data for the use of ACZ concurrently with high dose loop diuretics as well as data on the tolerability of treatment for a future trial.

	Asymptomatic hypotension (systolic blood pressure (SBP) <90 mmHg)
	Symptomatic hypotension (SBP <90 mmHg and symptoms of: dizziness or presyncope)
	Asymptomatic hyponatraemia (serum sodium concentrations <130 mmol/L)
Adverse Events	Symptomatic hyponatraemia (serum sodium concentrations <130 mmol/L and symptoms of fatigue, nausea, vomiting, or headache not promoting further treatment or investigation)†
	Flare of gout requiring oral treatment and analgesia
	Decrease in estimated glomerular filtration rate >50% of baseline value
	† Treatment of headache with analgesia not included in this definition however treatment of nausea or vomiting with antiemetic is.
	Symptomatic hypotension with sequelae (SBP <90 mmHg and symptoms of: dizziness or presyncope and fall or injury as a direct result)
	Symptomatic hyponatraemia with sequelae (serum sodium concentrations <130 mmol/L and symptoms of fatigue, nausea, vomiting, headache which prompt further treatment or investigation,† or confusion or seizure deemed secondary to hyponatraemia).
	Decrease in eGFR >100% of baseline value or serum creatinine >221µmol/L
	Deterioration in condition during trial defined as:
Serious Adverse Events	
 
Deemed to need escalating doses of loop diuretic or the addition of a second diuretic agent such as thiazide diuretic.
 
Deemed to need inotropic support
 
New diagnosis of infection
 
New diagnosis of another concurrent illness that will prolong hospital stay
 
Transition to end-of-life care
 
Death
 

	Overdose of ACZ or furosemide infusion defined as 1) >500mg given per day of ACZ or 2) >240mg IV furosemide per day.
Adverse Reactions	Metabolic acidosis bicarbonate <23 mmol/L
	Hyperchloraemia 107-110 mmol/L

	Teaching Hospi	tals
	Any of the following possible side effects of acetazolamide that are NHS tolerable to the patient: haemorrhage, ataxia, depression, diarrhoea,	Trust

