# 9.4 Reporting of SAEs AND SUSARs

All SAEs, SARS and SUSARs (except those defined as not requiring expedited reporting) will be reported to the Sponsor using the study specific SAE report form, within 24 hours of the research staff becoming aware of the event.

For each reported SAE the following information will be collected:

- full details in medical terms and case description
- event duration (start and end dates, if applicable, and if admitted, admission and discharge dates, with specialty noted)
- action taken
- outcome
  - seriousness criteria
    - causality (i.e. relatedness to trial drug / investigation), in the opinion of the investigator
- whether the event would be considered expected or unexpected.

Assessment of severity, seriousness and causality will be made by the PI or another authorised study doctor. The PI or authorised study doctor will need to decide whether the serious event is an SAE or SAR by assessing whether the event is either unrelated or possibly related to the IMP (causality). If the event is possibly related then it is a SAR and an assessment needs to be made by the Sponsor as to whether the event is expected or not for the IMP. If the SAR is listed in Section 4.8 of the MHRA approved Summary of Product Characteristics then it is expected.

In addition to the PI, the Sponsor will also be required to assess causality and document their assessment on the SAE form. The Sponsor must assess causality after the PI and must confirm that they

have not influenced the PI. The PI's assessment of causality must not be downgraded by the Sponsor.

If an authorised study doctor is unavailable, initial reports without the causality assessment will be submitted to the Sponsor by a healthcare professional within 24hours of becoming aware of the SAE, but will be followed-up by medical assessment as soon as possible thereafter. The PI must always review the SAE form and sign to confirm the contents of the report are accurate and complete and that he/she has also assessed the severity, seriousness and causality of the SAE.

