# 9.10 Reporting urgent safety measures

If any urgent safety measures are taken the PI/Sponsor shall immediately and in any event no later than 3 days from the date the measures are taken, give written notice to the MHRA and the relevant REC of the measures taken and the circumstances giving rise to those measures. Fatal SUSARs will be reported within 7 days, non-fatal SUSARs reported within 14 days.

https://www.gov.uk/guidance/clinical-trials-for-medicines-manage-your-authorisation-report-safetyissues#report-an-urgent-safety-issue

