# 9.11 The type and duration of the follow-up of subjects after adverse events.

Follow up for any AE, SAE, AR or SAR will be until the event has resolved or 30 days after baseline. This follow up will be via telephone consultation and the written and electronic record. Any SUSAR related to the IMP will need to be reported to the Sponsor irrespective of how long after IMP administration the reaction has occurred.

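### Section 9.7 fixes out-patient deaths to reports at 30 and 180 days, so a death learned of between those checks has two conflicting reporting times

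*Protocol*

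**What the plan says.** - **Section 9.7** commits to telling the sponsor of every death, on two timetables: "all in-patient deaths will be reported within 24 hours", but "all out-patient deaths will be reported at 30 and 180 days". Neither awareness nor relatedness is mentioned for the out-patient group.
- **Section 9.1** counts an event that "results in death" as serious. **Section 9.2** lists death among the serious adverse events and adds: "All serious adverse events serious adverse reactions, and suspected unexpected serious adverse reactions will be reported".
- **Section 9.4** gives the general rule: "All SAEs, SARS and SUSARs (except those defined as not requiring expedited reporting) will be reported to the Sponsor", and the time allowed is "within 24 hours of the research staff becoming aware of the event".
- **Section 9.6** makes the principal investigator responsible for SUSARs reaching the sponsor within 24 hours of awareness.
- **Section 9.11** requires any SUSAR related to the study drug to be reported "irrespective of how long after IMP administration the reaction has occurred".
- **Section 9.5** sets a 5-day monitoring period from baseline and collects adverse-event data up to discharge.
- **Section 7.8** plans the outcome checks: a telephone and records check at 30 days and a records check at 180 days.

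**The concern.** The same event has two reporting times. A participant is discharged, dies on day 35, and the study team hears of it that week. Under 9.4 the sponsor should know within 24 hours; under 9.7 the report is due at the 180-day check. Staff following 9.7 to the letter would breach 9.4, and staff following 9.4 would be ignoring the only section written specifically about deaths.

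The stake is the timing of safety review. The sponsor's causality and expectedness assessments (9.4, 9.6) cannot start until a report arrives. A death cannot be classified as a SUSAR, or as not one, before those assessments are made. Section 9.6 relies on continuing risk/benefit review, and 10.5 plans no interim analysis that would otherwise bring deaths together. Sections 9.2 and 9.4 also treat any serious adverse reaction seen in more than 5% of patients as a SUSAR. That is a running count, and a late report would hold it back.

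**Working it through.** **1. Is an out-patient death inside the reporting rules?** Yes, by 9.1 and 9.2. Section 11.4 ends the trial at the last patient's last visit, so the period to day 180 lies within the trial.

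**2. Does anything exempt it from the 24-hour rule?** Two candidates:
- The exception in 9.4 needs a definition of the exempt events, and section 9 contains none. If 9.7 is taken as that definition, it exempts every out-patient death, including one possibly related to the drug. That does not fit 9.6 and 9.11.
- Section 9.5 ends adverse-event collection at discharge but does not say that deaths after discharge are exempt. Section 9.7 itself says that all deaths go to the sponsor.

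**3. When do the two rules differ?** The 9.4 clock starts at awareness.

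| Situation | Due under 9.4 | Due under 9.7 | Conflict |
|---|---|---|---|
| Death first found at the day-30 or day-180 check | 24 hours after the check | at the check | none of substance |
| Death learned of after discharge, before day 30 | 24 hours | day 30 | yes |
| Death learned of after day 30, before day 180 | 24 hours | day 180 | yes |

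Earlier awareness is realistic. Section 13.10 says that most participants will go on using this hospital's emergency and routine care, and it plans a call within 30 days of discharge. With discharge on day 9, that call could fall as late as day 9 + 30 = 39, after the day-30 check. Section 9.11 also follows open events by telephone and records up to day 30.

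**4. Longest wait under 9.7.** Wait = check day − day of death, for a death known at once. The discharge day is an assumption: day 9 (the median stay in section 2) or day 5 (the end of the study visits).
- Before day 30: 30 − 9 = 21 days, or 30 − 5 = 25 days.
- After day 30: 180 − 30 = 150 days.

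These are maxima, not averages.

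**5. How many deaths are out-patient deaths?** Section 9.7 expects up to 4 deaths in hospital and a further 5 in the month after discharge.
- In hospital: 10% × 40 = 4, which reproduces the stated figure.
- After discharge: 25% × (40 − 4) = 9, not the stated 5; 5/36 is 13.9%. This is a separate slip in the same paragraph.
- Out-patient share: 5/(4 + 5) = 56% on the stated counts, and 9/(4 + 9) = 69% on the stated rates.

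Deaths from then to day 180 are expected but not counted. None of these figures says how many deaths would be learned of between checks.

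**The case against.** The best defence reads 9.7 as a specific rule beside a general one. Post-discharge deaths are anticipated, they form part of a secondary endpoint (3.5, item 16), and they are collected from records at the two follow-up points, after the adverse-event window in 9.5 has closed. On that reading 9.7 is the exception that 9.4 refers to, while 9.6 and 9.11 still catch a drug-related death. Treatment also lasts only 4 days and the stated half-life is 4 hours (8.5), so a death months later says less about the drug.

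Part of this stands. The awareness clock removes any conflict for deaths first found at a check, and nothing in 9.7 claims to override 9.6 or 9.11. But the exemption has to be inferred, because no section states it. Relying on 9.6 and 9.11 is also circular: a death is recognised as a SUSAR only after the causality and expectedness assessments that the report sets in motion.

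Three stronger readings are tempting and not supported:
- *Most expected deaths will be reported late.* The 56% to 69% is the out-patient share of expected deaths, not the share learned of between checks, which the protocol does not give.
- *A whole planned sample could be enrolled during one delay.* Two patients a week (10.2) over 150 days gives 150/7 × 2 ≈ 43. But by the first participant's day 30 about 30/7 × 2 ≈ 9 are already in, so at most about 31 of 40 remain, and fewer for later participants.
- *The 7 days in 9.10 is a third competing deadline.* "Fatal SUSARs will be reported within 7 days" stands in a section on notices to the MHRA and REC. It is a later step than the report to the sponsor.

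**Conclusion.** The concern holds in a limited form. As written, 9.7 conflicts with 9.4 for out-patient deaths that the study team learns of between the scheduled checks, and it makes no provision for one that may be drug-related. Following 9.7 literally, such a death could wait up to about 3 weeks if it occurs before day 30 (21 days with discharge on day 9, 25 with discharge on day 5), or up to about 150 days if it occurs after day 30. The month-long waits apply only to deaths after day 30, which the protocol expects but does not count.

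The number of deaths affected cannot be derived from the protocol. Out-patient deaths are 5 of the 9 it expects to about a month after discharge, so the group that the rule covers is not marginal. The conclusion rests on the absence of any definition of the events that 9.4 exempts. If such a definition exists in a sponsor procedure, the protocol should cite it. The point deserves correction because it governs what the sponsor knows, and when; it is not evidence that deaths will go unreported.

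**What to change.** Reconcile 9.4, 9.5, 9.7 and 9.11:
- In 9.7, state that any out-patient death is reported to the sponsor within 24 hours of the study team becoming aware of it and assessed for causality as in 9.4. State also that days 30 and 180 are the latest points at which deaths are ascertained, not the reporting dates.
- In 9.4, define the events exempt from expedited reporting, or remove the exception.
- In 9.5, say that the cut-off at discharge does not apply to deaths, and keep 9.11 as it is.

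While 9.7 is open, bring the expected 5 post-discharge deaths into line with the 25% rate given beside it.

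The reporting change applies the protocol's own 24-hour rule. It adds no visit and changes no treatment; its cost is one sentence, short consequential edits, and a few serious adverse event forms completed earlier than now planned.

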# 9.8 Pregnancy reporting

If a study patient, or the partner of a study patient, falls pregnant when participating in a clinical trial, the study patient should be withdrawn from the trial unless the Principal Investigator decides that the risk to the patient is not clinically significant.

The patient, or the partner of the study patient, should be followed up by monthly or two monthly visits/telephone contacts during pregnancy and at birth and at 3 months after the birth of the baby. Whether the visits are every month or two months will depend on clinical judgement and will be agreed with R&D and documented in the TMF.

Pregnancy is not expected to occur or be diagnosed in a patient recruited to the study during the active phase of the trial. Pregnancies that occur during follow up will not be reported as they are unrelated to the endpoints.

# 9.9 Overdose

Any overdose of ACZ or furosemide will be reported as an SAE and recorded in the medical notes, CRF and deviation log as soon as the study doctor is alerted. The sponsor will be alerted within 24 hours of a suspected serious breach. Overdoses will be observed from the electronic prescribing record. A patient receiving an overdose will be removed from analysis and replaced. The incident will also be reported using the Hull University Teaching Hospital Trust incident reporting system – Datix.

# 9.10 Reporting urgent safety measures

If any urgent safety measures are taken the PI/Sponsor shall immediately and in any event no later than 3 days from the date the measures are taken, give written notice to the MHRA and the relevant REC of the measures taken and the circumstances giving rise to those measures. Fatal SUSARs will be reported within 7 days, non-fatal SUSARs reported within 14 days.

https://www.gov.uk/guidance/clinical-trials-for-medicines-manage-your-authorisation-report-safetyissues#report-an-urgent-safety-issue

